### 5.4.2.2.2. Sputum Culture Conversion in MGIT

The percentage of participants with sputum culture conversion (defined as 3 consecutive negative sputum cultures taken at least 25 days apart) in MGIT will be summarized by randomized treatment group through Week 24. After Week 24, the percentage of participants with sputum culture conversion in optional cohort will be also summarized.

Sputum culture conversion at Week 48 and Week 60: The percentage of participants who achieved sputum culture conversion at Week 24 and completed 48-week BDQ-containing regimen and achieved sputum culture conversion at Week 60 in Group A will be compared with the percentage of participants who completed 60-week standard of care(SOC) regimen and achieved sputum culture conversion at Week 60 in Group B using the Cochran-Mantel-Haenszel test stratified by region. For treatment regimen change prior to the analysis timepoints, both the strategies similar to the primary estimand and the supplementary estimand for the primary endpoint will be applied.

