### 9.4.4. Secondary Endpoints

- Sputum culture conversion in MGIT and 7H10 or 7H11 agar media (other than MGIT at Week 24).

The percentage of participants with sputum culture conversion (defined as 3 consecutive negative sputum cultures taken at least 25 days apart) in MGIT and 7H10 or 7H11 agar media will be calculated after Week 4. The percentage of participants who achieved sputum culture conversion at Week 24 and completed 48-week BDQ-containing regimen and achieved sputum culture conversion at Week 60 in Group A will be compared with the percentage of participants who completed 60-week SOC regimen and achieved sputum culture conversion at Week 60 in Group B using the Cochran-Mantel-Haenszel test stratified by region (Japan, non-Japan).

- Sputum culture negativity in MGIT and 7H10 or 7H11 agar media.

The percentage of participants with sputum culture negativity in MGIT and 7H10 or 7H11 agar media will be calculated at each visit after Week 2, respectively. A generalized linear model including treatment, region (Japan, non-Japan), time, and treatment-by-time interaction as fixed effects will be applied for the number of negative culture participants and the number of all participants at each timepoint and comparison between treatment groups will be performed using the appropriate contrast for the percentage of negative culture participants at Week 24.

- Time to sputum culture conversion in MGIT.

Time to sputum culture conversion in MGIT is calculated as the interval in days between the initiation date of the study intervention and the sampling date of the first of the 3 consecutive negative sputum cultures from sputum samples collected at least 25 days apart. Kaplan-Meier estimates will be generated for the time to sputum culture conversion up to Week 24 and Week 48. The difference between the treatment groups will be compared using the log-rank test stratified by region (Japan, non-Japan) for the time to sputum culture conversion up to Week 24. For

participants with no sputum culture conversion during the analysed period, time to culture conversion is censored on the last assessment day of the analysed period.

- Time to positivity in MGIT.

Time to positivity is calculated as the time required to positive signal in MGIT. A recent study showed a similar correlation between CFU and time to positivity with MAC.

- SGRQ.

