
 
Clinical assessment: To evaluate the efficacy of BDQ compared with rifamycin when administered as part of a treatment regimen with CAM and EB in adult participants with treatment-refractory MAC-LD.
 
	
 
Change from baseline in patient-reported health status on total score of SGRQ at Weeks 48 and 60.
 
Change from baseline in lung function parameters at Weeks 24, 48, and 60.
 
Percentage of participants who undergo a change in their MAC-LD treatment regimen by Week 24, by Week 48 (Group A) and by Week 60 (Group B).
 

 
Microbiological assessment: To evaluate the efficacy of BDQ compared with rifamycin when administered as part of a treatment regimen with CAM and EB in adult participants with treatment-refractory MAC-LD at Week 60.
 
	
 
Percentage of participants with sputum culture conversion (defined as 3 consecutive negative sputum cultures taken at least 25 days apart) in MGIT and 7H10 or 7H11 agar media at Week 60.
 

 
To evaluate the safety and tolerability of BDQ compared with rifamycin when administered as part of a treatment regimen with CAM and EB in adult participants with treatment-refractory MAC-LD.
 
	
 
Safety and tolerability based on assessment of AEs, clinical laboratory assessments, 12-lead ECG, vital signs, physical examination, visual examination, and audiology up to Week 60.
 

 
To evaluate the PK of BDQ (and metabolite M2), and CAM (and metabolite 14-OH-CAM [optional]).
 
	
 
PK exposures of BDQ (and metabolite M2 [optional]) at Day 1, Weeks 2, 8, 12, 24, and 48, and CAM (and metabolite 14-OH-CAM [optional]) at Day 1, Weeks 2, 8, 12, and 24.
 

Exploratory	

 
Clinical assessment: To evaluate the efficacy of BDQ compared with rifamycin when administered as part of a treatment regimen with CAM and EB in adult participants with treatment refractory MAC - LD assessed by QOL-B NTM module.
 
	
 
Change from baseline in patient reported health status on score of QOL-B NTM module at Weeks 24, 48, and 60.
 

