## 3. SAMPLE SIZE DETERMINATION

Based on the results of 2 clinical studies in AMK liposome inhalation suspension (ALIS, Arikayce®), (Phase 2 [[Griffith 2018](#)] and Phase 3 [[Olivier 2017](#)]) in an analogous population, it is

anticipated that the rifamycin-containing regimen in this study will have a sputum culture conversion rate assumed to be equal to 10% after 24 weeks of treatment.

A sample size of 124 participants (62 in Group A: the BDQ containing regimen, 62 in Group B: the rifamycin-containing regimen) will have a power of about 80% to show superiority for a 20% difference in proportion of participants having sputum conversion at Week 24 based on a chi-square test (at the 5% 2-sided significance level) on the intent-to-treat (ITT) population.

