## 5.4.2.2. Analysis Methods

### 5.4.2.2.1. Sputum Culture Conversion in 7H10 or 7H11 Agar Media

Sputum culture conversion at Week 24: The Cochran-Mantel-Haenszel test stratified by region (at the 5% 2-sided significance level) will be used to compare sputum culture conversion rate in MGIT at Week 24. The proportion of the subjects with sputum culture conversion at Week 24 will be summarized as randomized and the treatment difference with 2-sided 95% CI will also be presented. The definition of sputum culture conversion is described in Section 5.3.1.

Sputum culture conversion at Week 48 and Week 60: The proportion of participants who achieved sputum culture conversion of each treatment group (ie, as randomized) will be calculated with 95% CI. Participants requiring a treatment regimen change to individualized regimen will also be considered as nonconverters.

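### The Week 60 MGIT comparison requires Week 24 conversion in Group A only, so its CMH test compares different outcomes in the two arms and does not test the listed endpoint

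*SAP*

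**What the plan says.** SAP 1.1 lists as a secondary endpoint the percentage with sputum culture conversion "in MGIT and 7H10 or 7H11 agar media at Week 60". The definition is the same for both arms and carries no Week 24 or completion condition.

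The analysis differs. In SAP 5.4.2.2.2, Group A success means having "achieved sputum culture conversion at Week 24 and completed 48-week BDQ-containing regimen and achieved sputum culture conversion at Week 60 in Group A". The comparator percentage is that of "participants who completed 60-week standard of care(SOC) regimen and achieved sputum culture conversion at Week 60 in Group B". The two are compared by a region-stratified CMH test. Protocol 9.4.4 words Group A in the same way and sets it against "participants who completed 60-week SOC regimen and achieved sputum culture conversion at Week 60 in Group B". Neither document explains why only one arm carries the Week 24 condition.

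The SAP paragraph is labelled for Weeks 48 and 60 but defines no Week 48 comparison. Plain MGIT conversion by randomized group is promised there only through Week 24. For regimen changes, it asks for both a composite and a treatment-policy version.

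In the neighbouring SAP 5.4.2.2.1, headed for the agar media, the Week 24 test "will be used to compare sputum culture conversion rate in MGIT at Week 24".

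**The concern.** Consider one participant in each arm who is culture-positive at Week 24, converts at Week 36, stays on the assigned regimen to its planned end and is converted at Week 60. The Group B participant is a success and the Group A participant is a failure.

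Such cases can arise. Protocol 4.2 keeps Group A non-converters on their regimen to Week 48, and Protocol 4.1 moves those converted at Week 48 into drug-free follow-up. Protocol 4.1 and 4.2 also let Group B non-converters continue rifamycin.

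This is the only between-group test specified for Week 60 conversion. If its success definition differs by arm, the estimate cannot be read as a treatment effect on Week 60 conversion, whichever arm it favours.

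**Working it through.** **The plan's own figure.** SAP 3 assumes a "culture conversion rate assumed to be equal to 10% after 24 weeks of treatment" in the control arm and claims "a power of about 80% to show superiority for a 20% difference in proportion of participants having sputum conversion at Week 24". The test it names is an unstratified chi-square, two-sided at 5%, in the ITT set. With 62 per arm and 30% v 10%, the pooled-variance formula gives 80.3%, and exact binomial enumeration of the uncorrected chi-square gives 81.0%. The design figure reproduces. No power is stated for Week 60.

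**Inputs for Week 60.** From the documents: n = 62 per arm, two-sided 5%, 10% conversion at Week 24 under rifamycin. The rest are assumptions, because the documents give no figures:
- L: share of Week 24 non-converters who convert later and are converted at Week 60, equal in both arms (0 to 10%).
- s: share of Group B Week 24 non-converters who leave rifamycin and so count as failures (0 to 100%).
- All Week 24 converters complete treatment and stay converted.

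The test is run unstratified, because regional rates are not given.

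**Formulas**, with p the Week 24 rate in the arm:
- Rule as written: A = p; B = p + (1 − p)(1 − s)L.
- Week 24 condition in both arms: A = p; B = p.
- Week 24 condition in neither arm, switchers as failures: A = p + (1 − p)L; B = p + (1 − p)(1 − s)L.

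**Identical arms (p = 10%), rule as written, exact chances of a significant result:**

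| L | s | A | B | favours rifamycin | favours BDQ |
|---|---|---|---|---|---|
| 0 | any | 10% | 10% | 2.5% | 2.5% |
| any | 100% | 10% | 10% | 2.5% | 2.5% |
| 5% | 50% | 10% | 12.25% | 5.8% | 0.9% |
| 5% | 0 | 10% | 14.5% | 11.1% | 0.3% |
| 10% | 50% | 10% | 14.5% | 11.1% | 0.3% |
| 10% | 0 | 10% | 19% | 28.7% | 0.05% or less |

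Example (L = 10%, s = 50%): B = 0.10 + 0.90 × 0.50 × 0.10 = 0.145.

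**Completion rule alone.** With no late conversion, suppose a further 10% of Group B successes are lost in Weeks 48 to 60 because that arm must complete 60 weeks. Then A = 10% and B = 0.10 × 0.90 = 9%. The chances become 3.9% for BDQ and 1.6% for rifamycin, a slight tilt the other way.

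**Planning rates (30% v 10% at Week 24), s = 0, exact power:**

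| L | as written | condition in both arms | condition in neither arm |
|---|---|---|---|
| 5% | 30% v 14.5%: 55% | 30% v 10%: 81% | 33.5% v 14.5%: 71% |
| 10% | 30% v 19%: 29% | 30% v 10%: 81% | 37% v 19%: 61% |

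At s = 100% the written rule already gives 30% v 10% and 81%.

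**Check on the remedy, identical arms, L = 10%.** Dropping the Week 24 condition from both arms, with switchers as failures, gives 19% v 14.5% at s = 50% (9.3% for BDQ, 0.4% for rifamycin) and 19% v 10% at s = 100% (28.7% for BDQ). Keeping the condition in both arms gives 10% v 10%, with 2.5% each way, whatever L and s are.

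**The case against.** A reader might infer that the test is biased against bedaquiline outright. The documents do not support that. The Week 24 term matters only if Group B non-converters stay on rifamycin and then convert. Protocol 4.2.1 describes later conversion on standard therapy as unlikely. Those same participants are offered bedaquiline in the optional cohort, and Protocol 4.1 counts everyone who switches as a treatment failure. Group B must also complete 60 weeks against 48. Quoting 29% alone would pick the scenario in which nobody leaves rifamycin; with half leaving it is 11%. All of this stands.

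A reader might also infer that the listed endpoint is not analysed at all. That goes too far. SAP 5.4.2.2.1 gives as-randomized agar proportions with 95% CI at Weeks 48 and 60, Protocol 9.4.4 plans conversion percentages in both media after Week 4, and Kaplan-Meier estimates cover MGIT conversion to Week 48. The gap is narrower: the CMH test does not address the listed Week 60 endpoint, and the SAP's MGIT section gives no plain by-arm proportion after Week 24.

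The endpoint is also supportive, since SAP 5.4.1 defines no key confirmatory secondary endpoints. That limits the consequences. It does not make the two success definitions comparable, and low late conversion is an expectation without a figure.

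**Conclusion.** The point holds as a mismatch of definitions, which is on the page and needs no assumption. Only Group A carries the Week 24 condition, and the tested quantity is not the listed Week 60 endpoint.

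The condition can only lower the Group A rate. The net direction and size are not determinable from the documents. Over the assumed range, with identical arms and full retention of Week 24 converters, the chance of a significant result favouring rifamycin is 2.5% to 29%, against a nominal 2.5%. A stricter completion rule in Group B can tilt it slightly the other way. A test whose built-in shift depends on unknown quantities is hard to interpret whichever way it falls.

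The primary analysis and its power are unaffected. The MGIT wording in the agar section is a separate drafting error: taken literally, it leaves the agar Week 24 endpoint untested.

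**What to change.** 1. In SAP 5.4.2.2.2 and Protocol 9.4.4, use one success definition for the sustained-conversion test in both arms: Week 24 conversion, completion of the assigned regimen and Week 60 conversion. Late conversion and switching by Week 24 non-converters then do not affect it. The difference between 48 and 60 weeks to completion remains and should be stated when the result is reported.
2. Also report plain Week 48 and Week 60 MGIT conversion by randomized arm, with the difference and 95% CI. In the composite version, count non-completion and regimen change, including transfer to the optional cohort, as non-conversion. Keep the treatment-policy version that the SAP already names, and say how the completion requirement applies to switchers under it.
3. State beside the plain composite result that it can favour Group A, because Group B switchers are failures while Group A non-converters stay on drug to Week 48. For the same reason, simply deleting the Week 24 condition is not a neutral repair.
4. In SAP 5.4.2.2.1, correct the Week 24 test so that it names the 7H10 or 7H11 agar media instead of MGIT.

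The cost is SAP wording, matching wording in Protocol 9.4.4 and a few lines of derivation code. No new data are needed.

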### 5.4.2.2.3. Sputum culture negativity in MGIT and 7H10 or 7H11 agar media

The percentage of participants with sputum culture negativity in MGIT and 7H10 or 7H11 agar media will be also summarized at each visit after Week 2, respectively. After Week 24, the percentage of participants with sputum culture conversion in optional cohort will be also summarized.

Sputum culture negativity in MGIT at Week 24: The Cochran-Mantel-Haenszel test stratified by region (at the 5% 2-sided significance level) will be used to compare sputum culture negativity in MGIT at Week 24. The proportion of the subjects with sputum culture negativity at Week 24 will be summarized as randomized and the treatment difference with 2-sided 95% CI will also be presented. A generalized linear model including treatment, region (Japan, non-Japan), time, and treatment-by-time interaction terms will be applied for the number of negative participants and the number of all participants at each timepoint and comparison between treatment groups will be performed using the appropriate contrast for the percentage of negative participants at Week 24. If the subjects switch to individualized treatment regimen or to optional cohort, sputum culture should be considered as not negative.

**5.4.2.2.4. Time to sputum culture conversion in MGIT**

Kaplan-Meier estimates will be produced for the time to sputum culture conversion. The percentage of the number of the subjects with sputum culture conversion will be presented by treatment groups as randomized. The definition of the event is described in Section 5.4.2.1.

Kaplan-Meier curves will be also graphically presented. The difference between the treatment groups will be compared using the log-rank test stratified by region (Japan, non-Japan) for the time to sputum culture conversion up to Week 24.

**5.4.2.2.5. Time to positivity in MGIT**

Time to positivity will be descriptively presented by visit for the patients with positivity of sputum culture. The descriptive statistics will be summarized by treatment groups. For the subjects who switch from RFP-containing regimen to BDQ-containing regimen, time to positivity after Week 24 will be also summarized.

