## 9.2. Sample Size Determination

Based on the results of 2 clinical trials of ALIS (Phase 2 and Phase 3) in an analogous population, it is anticipated that the rifamycin-containing regimen in this study will have a sputum culture conversion rate assumed to be equal to 10% after 24 weeks of treatment.

A sample size of 124 participants (62 in Group A: the BDQ containing regimen, 62 in Group B: the rifamycin-containing regimen) will have a power of about 80% to show superiority for a 20% difference in proportion of participants having sputum conversion at Week 24 based on a chi-square test (at the 5% 2-sided significance level) on the intent-to-treat (ITT) population.

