## **5.4. Secondary Endpoints Analysis**

### **5.4.1. Key Confirmatory Secondary Endpoints**

No key confirmatory secondary endpoints are defined in this study.

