### **Time to positivity in MGIT**

Time to positivity is calculated as the time required to positive signal in MGIT. If the qualitative result is “Negative”, time to positive signal is set to 42 (days). No imputation rules will be applied for withdrawn and missing data. If there are multiple positive samples, mean value will be used.

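### The SAP gives negative MGIT cultures a time to positivity of 42 days, then tabulates only culture-positive patients, so the by-arm summary compares subsets selected after randomisation

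*SAP*

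**What the plan says.** Time to positivity in MGIT up to Week 48 is a secondary endpoint under an objective that compares bedaquiline with rifamycin (Protocol section 3; SAP 1.1). Protocol 9.4.4 gives only a definition: "Time to positivity is calculated as the time required to positive signal in MGIT". It neither limits the endpoint to positive patients nor says what a negative culture contributes, and it supports the measure by citing its correlation with colony counts.

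SAP 5.4.2.1 adds three rules:
- For a negative qualitative result, "time to positive signal is set to 42 (days").
- Values lost through withdrawal or a missed sample are left missing.
- Where a visit yields more than one positive, the rule reads: "If there are multiple positive samples, mean value will be used".

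SAP 5.4.2.2.5 then sets the analysis: "Time to positivity will be descriptively presented by visit for the patients with positivity of sputum culture". The table is broken down by arm, as the section goes on to state: "The descriptive statistics will be summarized by treatment groups". No test is planned. SAP 5.4.1 states: "No key confirmatory secondary endpoints are defined in this study". SAP Appendix 2, which records departures from the protocol's analyses, lists only the dropped per-protocol set.

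**The concern.** The definition and the analysis do not fit together. A value for negatives is needed only if negatives enter the summary, and the analysis sentence appears to keep them out. Two programmers could build two different tables from these sections.

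The choice matters because culture status at a visit is itself an outcome of treatment. If bedaquiline turns more cultures negative, more of Group A leaves the table at each visit. What remains is a comparison of patients still positive in each arm, which randomisation does not protect. Time to positivity is also the one graded measure of bacterial load here, since Protocol 8.1.1 reads both the MGIT and the agar cultures as positive or negative. A table by treatment group will be read as a comparison whether or not a test accompanies it.

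**Working it through.** **The plan's own figure.** Protocol 9.2 assumes for control a "sputum culture conversion rate assumed to be equal to 10% after 24 weeks of treatment" and a 20-point difference, so 10% v 30%, two-sided 5%, about 80% power.

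n per arm = [1.960 × √(2 × 0.20 × 0.80) + 0.842 × √(0.10 × 0.90 + 0.30 × 0.70)]² / 0.20² = (1.109 + 0.461)² / 0.04 = 61.6, so 62. Power at 62 per arm is 80.3%. The stated sample size reproduces. Neither document gives a mean, SD or effect for time to positivity.

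**Inputs for time to positivity.** The 42-day value is the SAP's. The shares negative at a visit, pA = 0.30 and pB = 0.10, are an assumption: they are the planning rates for conversion (three consecutive negatives), used as a stand-in. The means among positives (mA, mB) and all distributions below are also assumed.

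**Who stays in the table.** 62 × 0.70 = 43.4 in Group A and 62 × 0.90 = 55.8 in Group B, so about 43 and 56.

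**Formula.** The mean over all cultures is p × 42 + (1 − p) × m. Hence:
- positives-only difference = mA − mB
- all-culture difference = (mA − mB) + pA(42 − mA) − pB(42 − mB)

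The positives-only figure is the smaller whenever pA(42 − mA) > pB(42 − mB). At 0.30 and 0.10 this is 12.6 − 0.3mA > 4.2 − 0.1mB, or mA < 28 + mB/3. With mB = 10 days, that means any mA below 31.3 days.

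| mA, mB (days) | All cultures, A − B | Positives only, A − B |
|---|---|---|
| 14, 10 | +9.2 | +4.0 |
| 10, 10 | +6.4 | 0 |
| 8, 10 | +5.0 | −2.0 |

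**Case 1: bedaquiline lengthens time to positivity throughout.** Latent times are log-normal with 10% (B) and 30% (A) beyond 42 days.

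| Log-scale SD | All cultures, A − B (days) | Positives only, A − B (days) | Loss |
|---|---|---|---|
| 0.4 | 6.57 | 4.41 | 33% |
| 0.6 | 8.12 | 5.15 | 37% |
| 0.8 | 9.09 | 5.48 | 40% |
| 1.2 | 9.99 | 5.41 | 46% |

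The difference shrinks and keeps its sign in every row.

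**Case 2: bedaquiline clears only the lowest-burden patients.** Both arms share one distribution (median 12 days, log-SD 0.6). The longest 30% become negative in A and the longest 10% in B.
- Positives only: 9.64 (A) v 12.01 (B), a difference of −2.4 days.
- All cultures: 0.30 × 42 + 0.70 × 9.64 = 19.3 (A) v 0.10 × 42 + 0.90 × 12.01 = 15.0 (B), a difference of +4.3 days.

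The sign flips, but only because those still positive were assumed to gain nothing. Since 12.01 / 9.64 = 1.245, lengthening their times by about 25% removes the reversal.

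**Case 2 with other spreads.** Set 10% of the control distribution beyond 42 days and take log-SD 0.5, 0.8 and 1.2. The positives-only difference is −3.55, −4.19 and −4.36 days with no benefit in the remaining positives. With a 1.5-fold lengthening in them it is +5.56, +1.61 and −1.05 days.

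**The case against.** Several counter-arguments have force.

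- **Another reading of the sentence.** The restriction could mean patients positive at some point. Inclusion criterion 5.2 requires a positive culture at screening, so the restriction would then exclude almost nobody and the 42-day rule would be in use. The by-visit wording favours positive at that visit but does not settle the matter. The text needs clarifying under either reading.
- **Consistency with the protocol.** A negative culture has no time to a positive signal, so a positives-only summary can be squared with Protocol 9.4.4. That is fair, but it cannot be squared with the SAP's own 42-day rule.
- **Negatives are analysed elsewhere.** Conversion (SAP 5.3.2.1), negativity by visit (5.4.2.2.3) and time to conversion (5.4.2.2.4) are all summarised by randomised group. A reader will see how many patients became negative in each arm. None of these measures load, so they do not repair this table.
- **Low stakes.** The summary is descriptive and no secondary endpoint is confirmatory. This stands and limits the weight of the point.

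A reader might infer that the rule does shrink or reverse the bedaquiline effect. The documents do not support that as fact: they give no distribution, no visit-level negativity rate and no bedaquiline effect for this endpoint. If bedaquiline does not change negativity, there is no selective loss of this kind. A reader might also say that the table drops treatment successes. One negative culture at one visit is not conversion, which needs three consecutive negatives at least 25 days apart.

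**Conclusion.** The inconsistency holds without any assumption: SAP 5.4.2.1 gives negatives a value that SAP 5.4.2.2.5, on its natural reading, never uses. The resulting by-arm table conditions on a post-randomisation outcome.

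The size is conditional. If bedaquiline raises negativity, shrinkage is the usual result: about a third to 40% for log-SDs of 0.4 to 0.8, and 46% at 1.2, under log-normal times and 30% v 10% negative at the visit. Reversal is a possibility confined to selective clearance with little effect in those still positive. It did not occur under uniform lengthening.

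This is worth correcting because the endpoint is a listed efficacy endpoint and the change is small. It does not bear on the primary analysis, power or type I error.

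**What to change.** In SAP 5.4.2.2.5:
1. Make the main by-visit summary all ITT participants with an evaluable MGIT culture at that visit. Enter negatives at 42 days as already defined, and treat that value as censored.
2. Report the numbers positive and negative, with median and quartiles, by arm. The quartiles are needed: in Case 2 both all-culture medians are 12 days, while the upper quartile is 42 days in A (30% are negative) and 12 × exp(0.674 × 0.6) = 18.0 days in B.
3. Keep the positives-only table as a supplement, labelled as conditional on positivity and not a randomised comparison.
4. State the value used when a visit yields one positive and one negative sample. Two samples are normally collected (Protocol Schedule of Activities, footnote m), and SAP 5.4.2.1 covers only several positives.
5. Say whether the same population applies to the post-Week 24 summary for patients who switch to bedaquiline.

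A rank test or censored-data comparison at Week 24 is optional, since neither document plans inference here. If the sponsor prefers positives only, the minimum is to delete the 42-day rule and label the table as in item 3.

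The cost is a few sentences in the SAP and a changed table filter. No new data are needed.
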